#### **SAD-HS:**

- EP547 25 mg (N = x)
- EP547 75 mg (N = x)
- EP547 225 mg (N = x)
- EP547 450 mg (N = x)
- EP547 TBD mg (N = x)
- Overall EP547 (N = xx)
- Overall Placebo (N = xx)

#### **MAD-HS:**

- EP547 25 mg QD (N = x)
- EP547 75 mg QD (N = x)
- EP547 TBD mg QD (N = x)
- Overall EP547 (N = xx)
- Overall Placebo (N = xx)

#### **SD-CP/SD-UP:**

CP EP547 TBD mg (N = x)

UP EP547 TBD mg (N = x)

**MAD-CP/MAD-UP:**

CP EP547 TBD mg QD (N = x)

CP EP547 TBD mg QD (N = x) (optional)

UP EP547 TBD mg QD (N = x)

UP EP547 TBD mg QD (N = x) (optional)

CP Overall EP547 (N = x) (optional)

UP Overall EP547 (N = x) (optional)

CP Overall Placebo (N = x)

UP Overall Placebo (N = x)

Placebo and active treatment groups will be pooled for all descriptive analysis for healthy subject segments. For MAD/CP and MAD/UP segments, placebo and active treatment groups will be pooled only if there are multiple dose levels. Continuous and Categorical analysis will be conducted as described in [section 3.1](#).

**3.7.2 PK outputs**

The same treatment group labels as mentioned in [section 3.7.1](#) will be used for all by-participant listings.

For summary separate tables will be provided for each segment (SAD-HS, MAD-HS, SD-CP/SD-UP, MAD-CP/MAD-UP) with the following treatment group labels:

**SAD-HS:**

EP547 25 mg (N = x)

EP547 75 mg (N = x)

EP547 225 mg (N = x)

EP547 450 mg (N = x)

EP547 TBD mg (N = x)

**MAD-HS:**

EP547 25 mg QD (N = x)

EP547 TBD mg QD (N = x)

EP547 TBD mg QD (N = x)

**SD-CP/SD-UP:**

CP EP547 TBD mg (N = x)

UP EP547 TBD mg (N = x)

**MAD-CP/MAD-UP:**

CP EP547 TBD mg QD (N = x)

CP EP547 TBD mg QD (N = x) (optional)

UP EP547 TBD mg QD (N = x)

UP EP547 TBD mg QD (N = x) (optional)

Continuous analysis will be conducted as described in [section 3.1](#).

### 3.7.3 Food Effect Segment

Separate tables and listings will be presented for FE segment.

All baseline, demographic, [REDACTED] tables will be presented by Sequence.

- Sequence 1 (N = x)
- Sequence 2 (N = x)
- Overall (N = x)

Where sequence 1 (Fasted for FE Period 1 followed by Fed for FE Period 2)  
sequence 2 (Fed for FE Period 1 followed by Fasted for FE Period 2).

All safety, analysis population, and PK tables will be presented by treatment.

- EP547 75 mg Fed (N = x)
- EP547 75 mg Fasted (N = x)
- Overall (N = x) [Only for AE, CM and analysis population table]

## 4. ANALYSIS POPULATIONS

In this study 4 analysis sets are defined: Enrolled, Safety, Pharmacokinetic (PK), and Pharmacodynamic (PD) population.

Furthermore, any additional exploratory analysis not identified in the SAP will be included in the final CSR as exploratory post hoc analyses, including analyses for additional study populations or subgroups of interest.

### 4.1 Population Descriptions

#### 4.1.1 Enrolled Population

This population will comprise all subjects who sign the informed consent form (ICF) to participate in the study, complete the screening visit procedures, and meet all eligibility criteria for enrollment.

All listings will be presented by the Enrolled Population.

#### 4.1.2 Safety Population

This population will comprise all subjects who receive at least 1 dose of study drug, whether prematurely withdrawn from the study or not and will be based on actual treatment received.

For FE segment, Safety Population will include all randomized subjects who receive any amount of study drug (EP547 75 mg Fasted or EP547 75 mg Fed) and will be based on the actual treatment received, if this differs from what the subject was randomized to.

All safety analyses will be based on the Safety Population.

#### 4.1.3 Pharmacokinetic (PK) Population

##### **Plasma PK population:**

Non FE segments: This population will comprise all subjects who receive at least one dose of study drug (EP547) and have any measurable plasma concentrations of EP547 and had no important protocol deviations affecting the pharmacokinetics of EP547 and for whom a sufficient number of samples are available to determine at least one PK parameter among  $C_{max}$ ,  $T_{max}$  and  $AUC_{0-t}$ . Subjects will be assessed on a subject-by-subject basis for inclusion in the PK Population and will be determined by the study and sponsor pharmacokineticist. The PK Population determination will be made before unblinding post database lock.

The PK analyses for EP547 and its metabolites (as applicable) will be conducted based on the PK Population for plasma concentration data.

For FE segment: This population will include all randomized subjects who receive at least one dose of study drug (EP547 75 mg Fasted or EP547 75 mg Fed) who had no important protocol deviations affecting the PK variables of EP547 and for whom a sufficient number of samples are available to determine at least 1 PK parameter among  $AUC_{0-t}$ ,  $C_{max}$  or  $T_{max}$ . All PK analysis will be based on this population. Subjects will be assessed on a subject-by-subject basis for inclusion in the PK Population and will be determined by the study and sponsor pharmacokineticist.

##### **Urine PK population:**

This population will comprise all subjects who receive at least one dose of study drug (EP547) and have any measurable urine concentrations of EP547 and had no important protocol deviations. The urine PK population determination will be made on subject-by-subject basis by the study and sponsor pharmacokineticist before unblinding post database lock.

The PK analyses for urine concentrations and parameters will be conducted based on the urine PK Population.

##### **Skin PK population:**

This population will comprise all subjects who receive at least one dose of study drug (EP547) and have any measurable skin concentrations of EP547 and had no important protocol deviations. The summary skin concentrations data of EP547 and its metabolites (as applicable) will be based on the PK population for skin concentration data.

The PK analyses for skin concentrations will be conducted based on the PK Population for skin concentration data.

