12.2. Urine Collection for Pharmacokinetics (SAD-HS Only)

Urine sampling for PK of EP547 will be collected at predose (-6 to 0 hours) and from >0 to 6, >6 to 12, and >12 to 18 hours postdose on Day 1; >18 to 24, >24 to 30, and >30 to 36 hours postdose on Day 2; and >36 to 42 and >42 to 48 hours postdose on Day 3.

12.3. Skin Biopsy for Pharmacokinetics (Last Dose Level for MAD-HS and All Dose Levels for MAD-CP and MAD-UP Only)

Given that EP547 is hypothesized to be an inverse agonist (inhibitor) of MRGPRX4 in the skin to reduce itch, three 3-mm biopsies of the skin from the back will be performed under local anesthesia on Day 1 at 2 hours postdose with an assessment window of +30 minutes. One biopsy will be used for PK to evaluate drug concentrations at the site of action and the other 2 biopsies will be used for PD assessment as described in Section 14.5 to further elucidate the mechanism of action of EP547.

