#### 3.1 General Considerations

All data collected on the electronic case report form (eCRF) will be presented in the data listings and will be listed and sorted by treatment group, participant number and visit, where applicable. All descriptive summaries will be presented by treatment group and nominal visit/time point (where applicable).

Unless otherwise stated, the following methods will be applied:

- Continuous variables: Descriptive statistics will include the number of non-missing values (n), arithmetic mean, standard deviation (SD), median, minimum and maximum values.

The minimum and maximum values will be displayed to the same decimal precision as the source data, the arithmetic mean, SD and median values will be displayed to one more decimal than the source data for the specific variable.

The appropriate precision for derived variables will be determined based on the precision of the data on which the derivations are based, and statistics will be presented in accordance with the above mentioned rules.

- PK data: The actual blood sampling dates and times relative to dosing time will be listed by treatment group, participant and nominal sampling time, with time deviation calculated, for all participants with available plasma concentration data, including participants excluded from the PK population. Individual (for each participant) and mean plasma and skin EP547 and metabolites (as applicable) concentrations over time will be displayed graphically in linear and semi-logarithmic plots of concentrations versus time. The actual collection time will be used for individual plasma and skin EP547 and metabolites (as applicable) concentration curves and the nominal time will be used for the plots of mean concentration curves.

For plasma and skin PK concentration data, the number of non-missing values, number of below limit of quantification (BLQ) values, arithmetic mean, standard deviation, median, minimum, maximum, coefficient of variation (CV%), geometric mean, geometric standard deviation (SD) and geometric coefficient of variation (geo CV%) values will be presented. For the calculation of summary statistics, unrounded data will be used and reported to three significant figures with the exception of n, n BLQ, and CV% which will be presented to the nearest integer and one decimal place, respectively.

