### 3.5 Handling of Missing Data

For the classification of Treatment emergent adverse event (TEAE) and Concomitant medication, the following will be applied in the following order:

- a. If all dates/times (start and stop) missing, the event/medication will automatically be classified as a TEAE/Concomitant medication.
- b. For adverse events (AEs) with a missing start date/time, if the event end date/time is prior to first study drug administration, the event will not be classified as a TEAE.
- c. If only the AE start year/ medication end year is present and is the same or is after the first study drug administration year unit, the event/medication will be classified as a TEAE/Concomitant medication.
- d. If the AE start month and year/medication end month and year are present and are the same or after the first study drug administration month and year units, the event/medication will be classified as a TEAE/Concomitant medication.

For the PK analysis the following will be applied:

- a. For the concentration descriptive summaries, concentrations may be excluded if sampling time deviation is considered large to affect the profile at the discretion of the pharmacokineticist.
- b. Concentrations (plasma and skin) that are below limit of quantification (BLQ which is 10 ng/mL undiluted) prior to the first quantifiable value will be set equal to zero. Post dose BLQ concentrations will be set to missing.
- c. Where there are no results (NR), these will be set to missing.
- d. If more than 75% of values per nominal timepoint and treatment group are BLQ, then all descriptive statistics, except for nBLQ, will be denoted as not calculable (NC).
- e. For the calculation and graphical representation (semi-log and log-log plots) of geometric descriptive statistics, 0 values will be set to missing.
- f. For the purpose of calculating the non-compartmental PK parameters, plasma concentrations that are BLQ prior to the first quantifiable value will be set equal to zero. BLQ values after measurable concentrations will be set to missing.
- g. For the calculation of summary statistics of PK parameters, all NR and NC values in a data series will be set to missing.

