### 10.3 Skin PK Analysis

All PK summary tables will be based on the PK Population for skin concentration data. All skin concentrations will be summarized as described in section 3.1 (PK - continuous descriptive analysis). A listing will be provided for the same based on the Enrolled Population.

For last dose level for MAD-HS and all dose levels for MAD-CP and MAD-UP, Skin EP547 and metabolites (as applicable) concentrations will be summarized.

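### The Skin PK population drops every subject whose single PK biopsy is BLQ, so the skin EP547 BLQ count is always 0 and the over-75% BLQ rule can never apply

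*SAP*

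**What the plan says.** - **Who is summarised.** SAP 4.1.3 defines the Skin PK population as subjects who took at least one dose of EP547 and "have any measurable skin concentrations of EP547 and had no important protocol deviations". The same section adds: "The summary skin concentrations data of EP547 and its metabolites (as applicable) will be based on the PK population for skin concentration data". SAP 10.3 repeats it: "All PK summary tables will be based on the PK Population for skin concentration data".
- **What is reported.** SAP 3.1 sets the statistics: "For plasma and skin PK concentration data, the number of non-missing values, number of below limit of quantification (BLQ) values", followed by the usual arithmetic and geometric summaries.
- **BLQ handling.** SAP 3.5(b) covers plasma and skin. Concentrations that are BLQ "prior to the first quantifiable value will be set equal to zero. Post dose BLQ concentrations will be set to missing". SAP 3.5(d) opens "If more than 75% of values per nominal timepoint and treatment group are BLQ" and in that case replaces every statistic except nBLQ with NC.
- **How skin is sampled.** Protocol 12.3 and Appendix B schedule three biopsies on one occasion, Day 1 at 2 hours postdose, in the last MAD-HS dose level and all MAD-CP and MAD-UP levels. Of these, "One biopsy will be used for PK to evaluate drug concentrations at the site of action"; the other two are for PD.
- **Where else the results appear.** The skin listing uses the Enrolled Population (SAP 10.3), and SAP 5.1.2 tabulates the number of subjects in each population.

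**The concern.** With one value per subject, the entry condition and the BLQ rules act on the same measurement. A BLQ biopsy removes the subject before the BLQ rules are reached, so the SAP promises two outputs for skin EP547 that its own population definition rules out.

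Skin concentration is a secondary outcome (Protocol 15.2.2), and the biopsy is meant to show drug where it is expected to act. The number of treated subjects with no quantifiable drug there is part of that answer, and it is the number the table cannot show. A subject who is BLQ for EP547 also takes any measurable metabolite (EP3583) value out of the summary.

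**Working it through.** The plan states no figure to reproduce on this point, so the check follows the definitions through every possible result.

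**Inputs**

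1. *Values per subject:* one PK biopsy. A second one through re-enrolment at another dose level is barred by Protocol 8.2.1 (criterion 11), 8.2.2 (criterion 13) and 8.2.3 (criterion 10).
2. *Meaning of measurable:* quantifiable. SAP 3.5(f) sets measurable concentrations against BLQ values, and the AUC0-inf definition in SAP 10.1 ties a measurable concentration to the quantification limit.
3. *EP547 subjects per biopsied level:* 6 in MAD-HS (Protocol 7.1.1). In MAD-CP and MAD-UP, 8 to 12 subjects at 3:1 in blocks of 4 (Protocol 7.1.2, 7.1.3, 9.3.1) give 6 to 9.

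**Step 1: enumerate.** With b of n biopsies BLQ, the Skin PK population holds n − b subjects, all quantifiable. Its nBLQ is 0 for every b below n, and at b = n it is empty. Among all EP547 subjects biopsied, nBLQ = b, and 3.5(d) applies once b/n > 0.75.

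| n | smallest b with b/n > 0.75 | share BLQ | subjects left in the SAP's table |
|---|---|---|---|
| 6 | 5 | 83.3% | 1 |
| 7 | 6 | 85.7% | 1 |
| 8 | 7 | 87.5% | 1 |
| 9 | 7 | 77.8% | 2 |

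For n = 6:
- With b = 1 to 4, nBLQ prints 0 instead of 1 to 4.
- With b = 5, it prints 0 with n = 1 and that single value as the mean, instead of nBLQ = 5 and NC.
- With b = 6, there is no one to summarise, instead of nBLQ = 6 and NC.

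**Step 2: how often.** The documents give no skin BLQ rate, so p, an independent chance of BLQ per biopsy, is an assumption.

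- Count not shown correctly: 1 − (1 − p)^n.
- Statistics printed where NC would be due: the sum of Binomial(n, p) probabilities from the threshold to n − 1 (5 only for n = 6; 7 and 8 for n = 9).

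| p | count wrong, n = 6 | count wrong, n = 9 | NC missed, n = 6 | NC missed, n = 9 |
|---|---|---|---|---|
| 0.10 | 0.469 | 0.613 | 0.00005 | <0.00001 |
| 0.25 | 0.822 | 0.925 | 0.0044 | 0.0013 |
| 0.50 | 0.984 | 0.998 | 0.094 | 0.088 |

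For example, at p = 0.50 and n = 6, the NC figure is 6 × 0.5^6 = 6/64 = 0.094.

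**Step 3: compare plasma.** The non-food-effect plasma population uses the same measurable clause without this effect, because each MAD subject has many samples (Protocol 12.1): 13 + 5 + 13 + 2 = 33 in MAD-HS, 13 + 1 + 1 + 13 + 2 = 30 in MAD-CP, and 3 × 13 + 1 + 13 + 2 = 55 in MAD-UP. Only a subject who is BLQ throughout is lost, so individual BLQ values remain to be counted.

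**Step 4: effect on the mean.** This depends on 3.5(b), which does not clearly settle a lone post-dose BLQ biopsy. Its first sentence can be read as giving zero and its second as giving missing. If missing, the mean is the same with or without the population clause up to 75% BLQ, and only nBLQ is affected. If zero, keeping BLQ subjects would multiply the printed mean by (n − b)/n; with 2 of 6 BLQ that is 4/6 = 0.67.

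**The case against.** The strongest reply is that nothing is miscalculated. SAP 3.5(d) names no population, section 10.3 assigns the Skin PK population, and inside it nBLQ = 0 is the true count. On that reading, shared plasma and skin rules merely become redundant for one analyte. This is consistent, but it empties provisions that name skin expressly (3.1 and 3.5(b)), and a reader would take nBLQ = 0 to mean that no biopsy was BLQ. The food-effect plasma population in the same section has no measurable clause, so the condition is not essential to a PK population.

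Other points stand in whole or part:

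- **The mean is probably unaffected.** Every biopsy is post-dose, so missing is the more natural reading of 3.5(b). Up to 75% BLQ, the error is then confined to the count.
- **BLQ may be rare.** Protocol 5.3 reports distribution to skin, about 0.8 L/kg volume, and a peak near 2 hours in monkeys. Assuming 70 kg, full absorption and that volume in humans, 225 mg/(0.8 × 70 L) is about 4,000 ng/mL in plasma and 25 mg about 450 ng/mL, against a 10 ng/mL limit. The skin-to-plasma ratio, any homogenate dilution and the patient MAD doses are not given, so this suggests but does not establish a low rate.
- **The results can be traced** through the Enrolled Population listing and the population counts.
- **No test or MAD-HS escalation depends on it.** The analysis is descriptive, and in MAD-HS only the last level is biopsied.
- **EP3583 is different.** Entry depends on EP547 alone, so the metabolite's nBLQ and 75% rule still work among the subjects who remain.

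**Conclusion.** The point holds for skin EP547 and is minor. As written, nBLQ is 0 in every non-empty group, and 3.5(d) cannot be triggered whatever the data show. This needs no distributional assumption; it rests on one assayed PK value per subject and on measurable meaning quantifiable, both of which the documents support.

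The wrong count is the likelier consequence, since a single BLQ biopsy produces it. Printing statistics from 1 or 2 subjects where NC is due matters only if BLQ is common: at most 0.0044 at p = 0.25, and about 0.09 at p = 0.50. Those probabilities depend on the assumed p and on independence between subjects. If no biopsy is BLQ, the tables are unchanged.

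**What to change.** In SAP 4.1.3, define the Skin PK population as EP547-treated subjects with an assayed PK skin biopsy result, measurable or not, and keep the existing protocol-deviation exclusion. Tables 14.2.5b and 14.2.5d then report n and nBLQ as section 3.1 intends, with 3.5(d) applied to them.

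Add one sentence to 3.5(b) stating how a lone post-dose BLQ biopsy is treated. If it is set to missing, label the mean as based on quantifiable values only and show nBLQ beside it.

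The cost is SAP wording and one population flag. No new data are needed, and no table changes unless a biopsy is BLQ.

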#### **4.1.4 Pharmacodynamic (PD) Population**

This population will comprise all subjects belonging to the Safety Population without major protocol deviations.

The PD analyses will be conducted based on the PD Population.

### **5. PARTICIPANT DISPOSITION AND ANALYSIS POPULATIONS**

Participant disposition and analysis population analyses will be based on the Safety and Enrolled population respectively. Participant disposition and analysis populations will be summarized descriptively as described in section 3.1 (categorical descriptive analysis). The screen failure including reason for screen failure will be presented in the by-participant data listings and will be summarized descriptively as described in section 3.1 (categorical descriptive analysis).

#### **5.1.1 Participant Disposition**

Participant disposition will include the number of participants who completed the study treatment as planned and completed the post-treatment follow-up, participants withdrawn from the study treatment and from post-treatment follow-up, as well as the primary reason for treatment termination and post-treatment follow-up termination. Participant disposition will be summarized descriptively.

#### **5.1.2 Analysis Populations**

The number of participants included in each study populations will be summarized descriptively.

In addition, the inclusion of each participant into/from each of the defined analysis populations will be presented in the by-participant data listings.

## **6. PROTOCOL DEVIATIONS**

Protocol deviations will be presented for each participant in the by-participant data listings and the classification and important protocol deviation will be summarized descriptively as described in section 3.1 (categorical descriptive analysis) under the Safety Population.

Prior to database lock, all protocol deviations will be tracked in the Novotech Clinical Trial Management System (CTMS). All important deviations are documented on an Important Protocol Deviation (IPD) form and are reviewed and approved by Novotech medical monitor and sponsor.

Protocol deviations and important protocol deviations will be categorized as noted in the protocol deviation management plan version 1.0 dated 2020-08-25.

## 7. DEMOGRAPHIC AND BASELINE INFORMATION

Demographic and baseline information analysis will be based on the Safety Population. If there is a difference from the Safety Population, demographic and baseline information analysis will be repeated for the PK and PD population.

Demographic and baseline information will be summarized descriptively as described in section 3.1.

### 7.1 Demographics and Baseline Characteristics

The following demographic and baseline characteristics parameters will be analyzed:

#### Continuous descriptive analysis:

- Age (years)
- Height (cm)
- Weight (kg)
- Body Mass Index (BMI) ( $\text{kg/m}^2$ ) =  $\text{weight (kg)} / [\text{height (m)}]^2$
- Estimated Glomerular Filtration Rate (eGFR) (only for UP segments)
- Child-Pugh Score (only for CP segments)

#### Categorical descriptive analysis:

- Sex
- Race
- Ethnicity
- eGFR (only for UP segments): G1 ( $\geq 90$ ), G2 (60 to 89), G3a (45 to 59), G3b (30 to 44), G4 (15 to 29), and G5 ( $< 15$ )
- Child-Pugh Score (only for CP segments): Class A (5 to 6 points), Class B (7 to 9 points), Class C (10 to 15 points)

Baseline eGFR will be derived using the CKD-EPI equation (Levey 2009)

$$\text{eGFR} = 141 \times \min(\text{SCr}/\kappa, 1)^\alpha \times \max(\text{SCr}/\kappa, 1)^{-1.209} \times 0.993^{\text{Age}} \times 1.018 [\text{if female}] \times 1.159 [\text{if Black}]$$

where

$$\text{eGFR (estimated glomerular filtration rate)} = \text{mL/min/1.73 m}^2$$

$$\text{SCr (standardized serum creatinine)} = \text{mg/dL}$$

$$\kappa = 0.7 \text{ (females) or } 0.9 \text{ (males)}$$

$$\alpha = -0.329 \text{ (females) or } -0.411 \text{ (males)}$$

min = indicates the minimum of  $\text{SCr}/\kappa$  or 1

max = indicates the maximum of  $\text{SCr}/\kappa$  or 1

age = years

